8.3.1. Time Period and Frequency for Collecting Adverse Event and Serious Adverse Event Information; 8.3.6. Adverse Events of Special Interest; 8.4. Treatment of Overdose; 10.4. Appendix 4: Adverse Events: Definitions and Procedures for Reporting, Evaluating, Follow-up, and Reporting; 10.7. Appendix 7: Thrombotic Events to be Recorded as AESIs	Details for AESI were added.	Added based on new risks and AESI included in Investigator Brochure and the amendment.
8.3.3. Follow-up of Adverse Events and Serious Adverse Events	Language added for the investigators to perform or arrange for the conduct of supplemental measurements and evaluations as medically indicated.	Added to clarify the investigators' responsibilities.

Section Number and Name	Description of Change	Brief Rationale
9.4. Statistical Analyses	Language added to create a separate analysis plan to support DRC meeting.	Added for clarification.
9.4.2. Primary Endpoint(s)	AESI was added for primary endpoints. Summary language added to include vital signs, physical examination and clinical safety laboratory assessments for safety assessment, and more detailed description for vital signs and Physical Examinations are removed.	Added based on change of primary endpoints in Section 3 Objectives and Endpoints of the amendment. Modified to clarify the additional safety analyses in addition to the primary endpoints listed for safety assessment.
10.1. Appendix 1: Abbreviations	Abbreviations were updated.	Updated based on changes in the amendment.
10.3. Appendix 3: Regulatory, Ethical, and Study Oversight Considerations	Language for use of Protocol Clarification Communications was added. Language added to allow remote consenting per local regulations. Language added on how the sponsor handles an event of a data security breach. AESI was added for data review by Data Review Committee.	Added based on process change per the sponsor. Added to allow flexibility on consenting method for participants and site staff. Added to clarify expectation in case of a data security breach. Added based on inclusion of AESI in Section 8.3.6 Adverse Event of Special Interest of the amendment.
10.4. Appendix 4: Adverse Events: Definitions and Procedures for Reporting, Evaluating, Follow-up, and Reporting	Reporting of participant pregnancy or participant partner(s) pregnancy was added as one of special reporting situations.	Added based on reporting requirement per the sponsor.
10.5. Appendix 5: Toxicity Grading Scale	Table B was added for laboratory abnormalities.	Added to provide guidance on assessment of clinical laboratory tests included in Appendix 6 Clinical Laboratory Tests and Section 8.3.6 Adverse Events of Special Interest added as part of this amendment, as well as other laboratory tests performed based on the investigator's judgment.
10.8. Appendix 8: Study Conduct During a Pandemic	New section added.	Added to clarify expectation on study conduct during Coronavirus Disease 2019 pandemic.
10.9. Appendix 9: Protocol Amendment History	Language updated to reference protocol amendment summary of changes table before the Table of Contents.	Updated to reflect amendment history.
11. References	New references added and reference format updated throughout the protocol amendment.	Updated based on review of references by the sponsor
Investigator Agreement	Sponsor's responsible medical officer was changed from [name] to [name].	Changed based on the sponsor team change

Section Number and Name	Description of Change	Brief Rationale
Throughout the protocol	Minor language updates were made for consistency and clarification.	Minor language updates made throughout the protocol to clarify and be consistent with the changes noted in the sections listed above.
Throughout the protocol	Minor grammatical, formatting, or spelling changes were made.	Minor errors were noted.

**VERSION HISTORY****Table 1 – SAP Version History Summary**

SAP Version	Approval Date	Change	Rationale
1.0	30-Nov-2023	Not Applicable	Initial release
2.0	06-Sep-2024	
Section 5.3.3: Updated the time to onset and duration of solicited AEs to present this information for all solicited AEs, not just the most frequent solicited AEs.
	Due to low sample size, all events will be included in this table.
		
Section 5.7.1.5.1: Updated table 5: full-length HA breadth panel to include Group 1 excluding H1 and Breadth coverage columns
	Table 5 updated to clarify which antigens are included in the extended breadth score analysis and in the analysis of the phylogenetic distance based weighting method.
		
Section 5.7.1.5.1: Add phylogenetic distance based weighting method for breadth panel summary. Added table 6: phylogenetic distance matrix. Added text to describe the analysis of extended breadth score, breadth coverage and extended breadth coverage. Described that the nasal antibody response will be performed on the same subset of subjects that are used for the analysis of the extended breadth ELISA panel. Also included information on nasal swab type.
	
This method combines the genetic distances between influenza HA antigens with the strength of the human sera to bind to these antigens. Table 6 is added to document the distance matrix used in the analysis. New additional analysis of the antigens included in the breadth panel, to account for all antigens of interest. Clarification for the analysis of the nasal antibody response.

		
Section 5.5: Corrected the number of items included in the Flu-iiQ impact categories
	Correction of typo in the number of items included in the Flu-iiQ impact categories.

## 1. INTRODUCTION

This is the statistical analysis plan (SAP) applicable for the VAC21148FLZ1001 trial and specifies the statistical methods for the planned analyses of safety, reactogenicity, and immunogenicity data collected in the study. The SAP (version 2.0) is based on Clinical Trial Protocol (CTP) VAC21148FLZ1001 Amendment 2. Titles, mock-ups, and programming instructions for all statistical outputs (tables, figures, and listings) will be provided in a separate document, the Data Presentation Specifications (DPS). This SAP will be finalized prior to the database lock for the final analysis.

### 1.1. Objectives and Endpoints

Refer to Section 3 of the CTP for a list of objectives and endpoints.

### 1.2. Study Design

Refer to Section 4.1 of the CTP for details on the study design, and section 6.3 of the CTP for details on randomization and procedures for maintaining the blind.

## 2. STATISTICAL HYPOTHESES

No formal statistical hypothesis on safety is to be tested. The study will evaluate whether INFLUENZA G1 mHA, with or without Al(OH)3 adjuvant, is safe, well tolerated, and immunogenic in healthy adults aged  $\geq 18$  to  $\leq 45$  years.

Safety data will be analyzed descriptively per vaccine group (placebo from Cohort 1 and 2 will be combined), with special attention to SAEs, Grade 3/4 AEs, and AEs leading to discontinuation of study vaccine.

No formal hypothesis on immunogenicity will be tested. Immunogenicity data will be analyzed descriptively per study group. Descriptive statistics (geometric mean and 95% CI, or median and quartile range [Q1-Q3], as appropriate) will be calculated for continuous immunological parameters at all time points and for changes from baseline.

## 3. SAMPLE SIZE DETERMINATION

Refer to Section 9.2 of the CTP for details.

## 4. POPULATIONS (ANALYSIS SETS) FOR ANALYSIS

Population	Description
Full Analysis Set (FAS)	The full analysis set will include all participants with at least one vaccination documented. All safety and participant information analyses will be based on the FAS.

Population	Description
Per-protocol Immunogenicity (PPI)	
The PPI population will include all randomized and vaccinated participants for whom immunogenicity data are available excluding samples taken on or after the date when a participant experiences a major protocol deviation expected to impact the immunogenicity outcomes.
 
In addition, samples obtained after missed doses or samples obtained after natural infection (if applicable) will be excluded from the analysis.
 
 
For participants who experience a natural influenza infection (based on RT-PCR, or other sources), samples collected within 7 days prior to and after the natural infection (e.g. start of reporting of ILI symptoms) will not be considered in the assessment of the immunogenicity of the selected regimen.
 
If a participant misses one or more active dose(s) of the selected regimen but continues the planned visit schedule, samples after the missed active dose(s) will not be considered.
 
 
The analysis of all secondary and exploratory immunogenicity endpoints will be based on the PPI set.
 
A sensitivity analysis may be performed to assess the impact of suspected sub-clinical influenza infection on immunogenicity. Suspected sub-clinical influenza infection will be defined at a given time point if a participant has a fold-increase from baseline for the full-length H5 ELISA four times greater than the fold-increase from baseline for the H5 VNA. Samples collected after suspected sub-clinical influenza infection will be excluded from this analysis.
 
Depending on the number of samples excluded, an exploratory analysis might be performed, including the excluded samples. To visualize excluded samples, participant profiles from several assays might be repeated, indicating the excluded samples.

Vaccine assignment will follow the as-treated principle (participant will be presented according to received vaccine group).

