Blood and urine samples for clinical laboratory assessments will be collected as indicated in Section 1.3 Schedule of Activities and Section 10.6, Appendix 6: Clinical Laboratory Tests.

Blood will be collected from all participants to assess humoral immune responses pre-vaccination on each dosing day, at 7 days and at 28 days after each dose, at 6 months after the second dose, and at 12 months after the first dose (or at the early exit visit if the participant prematurely terminates the study without withdrawing consent ^a).

Participants should record signs and symptoms of influenza during the influenza season using a specific Influenza Intensity and Impact Questionnaire (Flu-iiQTM) and an ILI form. Participants will be informed of the timing of the start and end of the influenza season in accordance with the country/region-specific influenza local surveillance system. Procedures for Flu-iiQTM questionnaire and ILI form completion are described in Section 8.1.1, ILI Procedures. The Flu-iiQTM questionnaire and ILI form will be the primary source for influenza monitoring. Participants will be contacted by telephone or other means of communication every 14±3 days (unless a planned clinic visit has occurred or will occur within 14 days). Calls will remind the participants to complete the Flu-iiQTM questionnaire and ILI form in the event of any symptoms of influenza infection, to contact the site at the time of symptom onset, and to take a nasal swab at home preferably on the day of symptom onset or the day thereafter (ILI Days 1-2). Calls will also check for any SAEs and associated concomitant medications since the previous visit or telephone contact.

Full details of ILI procedures, including the collection of nasal swabs are provided in Section 8.1.1, ILI Procedures.

The presence of influenza virus infection will be assessed by qualified site staff by RT-PCR diagnostics and/or rapid-PCR detection (eg, by Cepheid GeneXpert[®]) on the nasal swab samples.

Seasonal Influenza Vaccination

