6.4. Study Vaccine Compliance

Study vaccines will be administered intramuscularly by blinded qualified study-site personnel at the study site. Details of each administration will be recorded in the eCRF (including date and time of injection and location used for injection). For blinding procedures, see Section 6.3, Measures to Minimize Bias: Randomization and Blinding.

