The timings of the post-vaccination visits will be determined relative to the actual day of the corresponding vaccination. If a participant misses a vaccination, the post-vaccination visits will be calculated from the imputative vaccination date according to protocol.

Table 2: Visit Windows

VISIT	Visit Day	Window	Primary Purpose
Visit 1	Day -42 to 1	–	Screening visit
Visit 2	Day 1	–	FIRST STUDY VACCINATION
Visit 3	Day 8 (Vac 1+7 days)	+2 days	7-day post-first study vaccination safety and immunogenicity visit ^a
Visit 4	Day 29 (Vac 1+28 days)	±3 days	28-day post-first study vaccination safety and immunogenicity visit
Visit 5	Day 57	±3 days	SECOND STUDY VACCINATION
Visit 6	Day 64 (Vac 2+7 days)	+2 days	7-day post-second study vaccination safety and immunogenicity visit ^a
Visit 7	Day 85 (Vac 2+28 days)	±3 days	28-day post-second study vaccination safety and immunogenicity visit
Visit 8	Day 238 (Vac 2+6 months)	±14 days	6-month post-second study vaccination safety and immunogenicity visit
Visit 9	Day 365 (Vac 1+12 months)	±30 days	FINAL VISIT: 12-month post-first study vaccination safety and immunogenicity visit

^a Sentinel participants will additionally be contacted by telephone 48 hours post-vaccination to collect safety information.

Screening

Screening may be conducted in part via a sponsor- and IRB/IEC-pre-approved non-study specific screening consent process, but only if the relevant pre-screening tests are identical to the per-protocol screening tests and are within 6 weeks prior to first vaccination. However, no study-specific procedures, other than these pre-approved pre-screening assessments, will be performed until the participant has signed the study-specific ICF. The study specific ICF date will be entered into the eCRF. The non-study specific ICF will be considered source data.

Sample Collection and Handling

The actual dates and times of sample collection must be recorded in the eCRF or laboratory requisition form.

Refer to Section 1.3, Schedule of Activities for the timing and frequency of all sample collections.

Instructions for the collection, handling, storage, and shipment of samples are found in the laboratory manual that will be provided, or per the requirements of local laboratories. Collection, handling, storage, and shipment of samples must be under the specified, and where applicable, controlled temperature conditions as indicated in the laboratory manual, or per the requirements of local laboratories.

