#### **6.4. Appendix 4 Protocol Deviations**

Major protocol deviations will be summarized.

In general, the following list of major protocol deviations may have the potential to impact participants' rights, safety or well-being, or the integrity and/or result of the clinical study. Participants with major protocol deviations will be identified prior to database lock and the participants with major protocol deviations will be summarized by category.

- Developed withdrawal criteria but not withdrawn
- Entered but did not satisfy criteria
- Received a disallowed concomitant treatment
- Received wrong vaccination regimen or incorrect dose
- Other

Major protocol deviations which have a potential impact on immunogenicity will be flagged in the listings.

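### The per-protocol immunogenicity rule cuts by calendar date, so a second injection that is itself the impacting deviation also removes the valid Day 57 sample drawn before it

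*SAP*

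**What the plan says.** **Exclusion rule.** SAP section 4 builds the PPI set from randomized, vaccinated participants with immunogenicity data, "excluding samples taken on or after the date when a participant experiences a major protocol deviation expected to impact the immunogenicity outcomes". Protocol 9.3 has the same rule. The cut is by date, and the deviation date itself is included.

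**Sampling.** Protocol 4.1 has blood taken to "assess humoral immune responses pre-vaccination on each dosing day". The Schedule of Activities (Protocol 1.3.1) marks the Day 57 humoral serum as pre-dose. Protocol section 8, Table 2, labels that visit "SECOND STUDY VACCINATION".

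**Deviation categories.** SAP Appendix 4 lists "Received wrong vaccination regimen or incorrect dose" among the major deviations. Those with a potential impact on immunogenicity are flagged separately.

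**Missed doses.** The neighbouring rule in SAP section 4 is worded differently: "samples after the missed active dose(s) will not be considered".

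**Recorded times.** Protocol section 8 states: "The actual dates and times of sample collection must be recorded in the eCRF or laboratory requisition form". Protocol 6.4 requires administration details "including date and time of injection and location used for injection".

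No section of either document exempts a pre-dose sample from the date rule.

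**The concern.** The purpose of the exclusion is to keep out samples that the deviation could have altered. A sample drawn before the injection cannot have been altered by an error in that injection, so dropping it gains no validity.

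The rule also sits awkwardly with the rest of the SAP:

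- SAP Table 2 references Day 57 to the first vaccination, and Days 64, 85 and 238 to the second. The SAP therefore treats Day 57 as a response to Dose 1.
- The phase definitions in SAP 5.1.2 start the second post-dose period at the date and time of the second injection. An adverse event that begins just before that injection is allocated to an earlier period, while a serum sample drawn at that moment is lost to a Dose 2 error.
- On the wording of the missed-dose rule, a participant who attends, is bled and then misses an active Dose 2 keeps the Day 57 sample. A participant given a wrong Dose 2 judged to impact immunogenicity loses it.

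At stake is a small amount of secondary-endpoint data at one time point. SAP section 4 bases all secondary and exploratory immunogenicity analyses on the PPI set, and SAP section 2 summarises continuous parameters at every time point.

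**Working it through.** **1. The plan's own figures.** Protocol 9.2 assumes about 12% lost from 25 per regimen: 25 × (1 − 0.12) = 22, as stated. Table 5 there reproduces with a two-sample t-test, n = 22 per group, two-sided alpha 0.05. For a 2-fold difference at SD 0.301 the result is 89.97% against 90.0% printed. The largest gap is 88.3% against 88.5% (1.5-fold, SD 0.181). All 18 non-null cells agree within 0.2 points. The 12% pools dropout with every impacting major deviation, so it does not give a rate of Dose 2 errors.

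**2. Samples lost to one participant.** The schedule has eight humoral time points. Suppose the second injection on Day 57 is a major deviation judged to impact immunogenicity.

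| Time point | Current date rule | With a pre-dose exemption |
|---|---|---|
| Day 1, Day 8, Day 29 | kept | kept |
| Day 57 (pre-dose) | dropped | kept |
| Day 64, Day 85, Day 238, Day 365 | dropped | dropped |
| Total kept / dropped | 3 / 5 | 4 / 4 |

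The difference is exactly one sample.

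**3. Effect on the Day 57 interval.** The half-width of the 95% interval for the mean log10 value is t(0.975, n − 1) × SD / √n. With k of 25 samples dropped and the same SD, the ratio of half-widths is

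[t(0.975, 24 − k) / √(25 − k)] / [t(0.975, 24) / √25].

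The denominator is 2.0639 / 5 = 0.4128. The values of k are assumptions, because the documents give none.

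| k | t / √n | Ratio | Widening |
|---|---|---|---|
| 0 | 2.0639 / √25 = 0.4128 | 1.000 | 0% |
| 1 | 2.0687 / √24 = 0.4223 | 1.023 | 2.3% |
| 2 | 2.0739 / √23 = 0.4324 | 1.048 | 4.8% |
| 3 | 2.0796 / √22 = 0.4434 | 1.074 | 7.4% |

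Back-transformed, the factor either side of the geometric mean, 10^(half-width), at the smallest and largest SDs in Protocol Table 5 is:

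| k | SD 0.181 | SD 0.783 |
|---|---|---|
| 0 | 1.188 | 2.105 |
| 1 | 1.192 | 2.141 |
| 2 | 1.197 | 2.181 |
| 3 | 1.203 | 2.224 |

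Starting from 25 assumes that everyone else in the group has a usable Day 57 value. With fewer, each lost sample costs slightly more in relative terms.

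**4. What is not touched.** For a Dose 2 deviation, baseline, Day 8 and Day 29 are kept under either rule. The external-control comparison in SAP 5.7.1.6.2 uses 28 days after Dose 1. The minimum time points for the correlation plots in SAP 5.7.1.5.1 are baseline and Day 29.

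**The case against.** The best defence is that a date cut is unambiguous and reproducible, costs at most one sample per affected participant, and is the same in protocol and SAP. No bias has been shown, and no immunogenicity hypothesis is tested. SAP section 4 allows an exploratory analysis with excluded samples restored, and Protocol 9.4.3 allows an additional analysis on the full analysis set. This supports keeping a date-based rule and rating the point as minor. It does not answer it: both extra analyses are optional, and restoring all excluded samples would also bring back those the deviation did affect.

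The rule is also narrower than it may look. A reader might infer that every Dose 2 deviation costs the Day 57 sample. The documents do not support that, because only major deviations expected to impact immunogenicity count. Under as-treated assignment (SAP section 4) some errors may not be judged impacting. For example, a Group 4 participant given placebo at Dose 2 has received the Group 6 regimen. Nor do mistimed doses add much: SAP Table 2 already removes Day 57 samples outside relative days 47 to 67.

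A reader might also infer that Day 57 is the last single-dose time point in every regimen, so that the loss weakens the comparison of one dose with two. It does not. Groups 6 and 7 receive placebo on Day 57 and supply single-dose data through Day 365, and Groups 3 and 8 are placebo throughout. At the high dose, one against two doses is a randomized comparison of Groups 6 and 7 with Groups 4 and 5.

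The contrast with missed doses is not guaranteed either: a missed dose might be classed as a major deviation under the residual category in SAP Appendix 4. That would remove the contrast but leave the main point.

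**Conclusion.** The point holds as a minor drafting flaw. Read literally, SAP section 4 and Protocol 9.3 remove a valid Day 57 pre-dose sample when the second injection is itself a major deviation judged to impact immunogenicity, and nothing in either document exempts it. The loss is one sample per affected participant and reaches only the Day 57 summaries. With an assumed 1, 2 or 3 such participants in a group of 25, the Day 57 interval widens by about 2.3%, 4.8% or 7.4%; with none, nothing is lost. These figures assume an unchanged SD and otherwise complete Day 57 data. The point concerns needless loss of precision at one time point and gives no ground for doubting the regimen comparison.

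**What to change.** Keep the date-based rule and add one sentence to SAP section 4, with the same sentence in Protocol 9.3 at any next amendment:

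*A pre-dose sample on a dosing day is retained when the deviation is the vaccination given that day.*

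The cost is that sentence and one condition in the derivation of the PPI flag. Sample and injection times are already recorded, so the order of the two can be verified.

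A general cut by date and time should not replace the date rule. Only sample and injection times are shown to be recorded. Other listed deviations, such as a disallowed treatment or an unmet entry criterion, have no stated clock time, and same-day samples would become undetermined where the present rule is clear.

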
 • Exploratory objective: To evaluate longevity of immune responses elicited by INFLUENZA G1 mHA, with or without Al(OH)₃ adjuvant in participants aged ≥ 18 to ≤ 45 years. 	
 • Exploratory endpoint: The magnitude and functionality of antibodies binding to the stem or the full-length HA protein of various strains as measured by ELISA, virus neutralization assays, and FcγR binding assays on Days 238 and 365.

 • Exploratory objective: To evaluate the immune responses in participants with confirmed influenza infection. 	
 • Exploratory endpoint: During the influenza season: 
 – Immune responses by assays included for secondary and exploratory immunogenicity endpoints
Virology	

 • Exploratory objective: To monitor symptoms of influenza-like illness (ILI) via the Influenza Intensity and Impact Questionnaire (Flu-iiQTM) as well as rapid molecular diagnosis and characterization to evaluate infection rate in participants aged ≥ 18 to ≤ 45 years and in relation to immunological markers. 	
 • Exploratory endpoints: During the influenza season: 
 – Signs and symptoms of ILI – Confirmation of infection by reverse transcriptase polymerase chain reaction (RT-PCR) or response to influenza-like infection by serology

Refer to Section 8, Study Assessments and Procedures for evaluations related to endpoints.

HYPOTHESIS

No formal statistical hypothesis is to be tested. The study will evaluate whether INFLUENZA G1 mHA, with or without Al(OH)₃ adjuvant, is safe, well tolerated and immunogenic in healthy adults aged ≥ 18 to ≤ 45 years.

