9.3. Populations for Analyses

For purposes of analysis, the following populations are defined:

Population	Description
Full Analysis Set (FAS)	
The full analysis set will include all participants with at least one vaccination documented.
 
All safety and participant information analyses will be based on the FAS.

Per-protocol Immunogenicity (PPI)	
The PPI population will include all randomized and vaccinated participants for whom immunogenicity data are available excluding samples taken on or after the date when a participant experiences a major protocol deviation expected to impact the immunogenicity outcomes.
 
In addition, samples obtained after missed doses or samples obtained after natural infection (if applicable) will be excluded from the analysis.
 
 For participants who experience a natural influenza infection (based on RT-PCR, or other sources), samples collected at and after the natural infection will not be considered in the assessment of the immunogenicity of the selected regimen.

Population	Description
	
• If a participant misses one or more active dose(s) of the selected regimen but continues the planned visit schedule, samples after the missed active dose(s) will not be considered. 
The analysis of all secondary and exploratory immunogenicity endpoints will be based on the PPI set. Depending on the number of samples excluded, a post-hoc exploratory analysis might be performed, including the excluded samples. To visualize excluded samples, participant profiles from several assays might be repeated, indicating the excluded samples.

Vaccine assignment will follow the as-treated principle.

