**6.2. Appendix 2 Changes to Protocol-Planned Analyses**

None to describe at the drafting of SAP version 1.0.

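### SAP section 4 contradicts itself on samples taken after natural influenza infection, and one literal reading would keep nearly all late post-infection samples in the per-protocol durability analysis

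*SAP*

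**What the plan says.** **Protocol 9.3.** The PPI definition excludes samples obtained after natural infection. Its bullet spells this out: "samples collected at and after the natural infection will not be considered in the assessment of the immunogenicity of the selected regimen". There is no end date and no look-back before onset.

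**SAP section 4, lead sentence.** The SAP repeats the protocol's general rule: "In addition, samples obtained after missed doses or samples obtained after natural infection (if applicable) will be excluded from the analysis".

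**SAP section 4, bullet.** The detail under that sentence differs from the protocol. It removes "samples collected within 7 days prior to and after the natural infection", and gives the start of symptom reporting as an example of the infection date.

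**SAP section 4, sub-clinical infection.** For an optional sensitivity analysis in the same table cell, the rule has no end date: "Samples collected after suspected sub-clinical influenza infection will be excluded from this analysis".

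**Use of the set.** The SAP states: "The analysis of all secondary and exploratory immunogenicity endpoints will be based on the PPI set". Protocol section 3 defines the exploratory longevity endpoint by ELISA, virus neutralization and "FcγR binding assays on Days 238 and 365". SAP Table 4 places H5 ELISA durability in the core assay package.

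**Record of changes.** SAP Appendix 2 reads: "None to describe at the drafting of SAP version 1.0". The SAP is now at version 2.0, and its version history does not mention the infection rule either.

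**The concern.** In ordinary usage, a sample within 7 days before and after an event lies inside a window closed on both sides. On that reading, a sample taken months after a confirmed infection is kept, although the protocol and the SAP's own lead sentence remove it. One table cell then supports two different PPI sets.

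The late visits are the ones exposed. Follow-up lasts about a year, with influenza-like illness surveillance during the season. Participants forgo seasonal influenza vaccine so that longevity can be assessed without that interference (protocol 4.1). An infection can disturb the late titres in the same way. Retained post-infection samples could make a regimen look more durable than it is. If they fell in the placebo group, they could shrink the active-to-placebo ratios. Immunogenicity results feed the choice of regimen (protocol 9.5, SAP 5.8).

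**Working it through.** No figure in the plan rests on this rule, so the check is a comparison of wording followed by an illustration of what turns on it.

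**1. The rules side by side.** Take a participant with a detected infection on Day 150. The neighbouring scheduled immunogenicity samples are Days 85, 238 and 365.

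| Rule | Days excluded | Day 238 and Day 365 samples |
|---|---|---|
| Protocol 9.3 bullet | Day 150 onward | dropped |
| SAP lead sentence | after Day 150 | dropped |
| SAP bullet, closed window | Days 143 to 157 | kept |
| SAP bullet, 7 days before plus everything after | Day 143 onward | dropped |

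On the closed window this participant loses no scheduled sample at all.

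**2. Share of post-infection samples kept on the closed window.** Assumption: the infection date is uniform between Day 85 and the sample. A sample is dropped only if infection fell in the 7 days before it.

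- Day 238: 7 / (238 − 85) = 7/153 = 4.6% dropped, 95.4% kept.
- Day 365: 7 / (365 − 85) = 7/280 = 2.5% dropped, 97.5% kept.

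Under the protocol rule or the open-ended reading, none are kept.

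**3. Possible effect on a group GMT.** Protocol 9.2 plans 25 per regimen less 12%: 25 × 0.88 = 22. If k of n participants carry a boost of b-fold, the GMT is multiplied by b^(k/n). The values of b and k are assumptions, and the boost is taken to persist in full to the sampling day.

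| Boosted participants (of 22) | 4-fold | 10-fold |
|---|---|---|
| 1 | 4^(1/22) = 1.07 | 10^(1/22) = 1.11 |
| 2 | 4^(2/22) = 1.13 | 10^(2/22) = 1.23 |
| 3 | 4^(3/22) = 1.21 | 10^(3/22) = 1.37 |

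A wider range, from one participant at 2-fold to four at 16-fold, gives 2^(1/22) = 1.03 to 16^(4/22) = 1.66. With no infections, no boost, or an open-ended exclusion, the factor from detected infections is 1.00.

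**4. The look-back.** Whichever way the bullet is read, it removes samples from the 7 days before onset. The protocol keeps those samples.

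**The case against.** The strongest reply is that the context already settles the meaning. The bullet elaborates a sentence that excludes all post-infection samples without limit, and its wording can be parsed as 7 days before, and any time after. That parse agrees with the protocol. It also agrees with the open-ended sub-clinical rule, which SAP 5.7.1 describes as removing additional samples. Dropping all later samples after a suspected infection while keeping most of them after a confirmed one would make little sense.

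This stands as far as intent goes. A reader might infer that the SAP has replaced the protocol rule with a 7-day window, or that the bullet is the rule that will be programmed. The documents support neither. The lead sentence is still there, nothing ranks the bullet above it, and SAP section 1 puts the programming instructions for outputs in the Data Presentation Specifications, which are not available here. The ambiguity remains, because the bullet's ordinary sense contradicts the sentence it is meant to explain, and it is the only text giving a number of days.

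The illustration is also open to fair criticism. Boost size and infection count are assumed. A boost may wane before sampling. Protocol 2.1 describes antibody binding that follows HA groups, so infection with a Group 2 or B virus may move the Group 1 H5 ELISA less. Twenty-two is a planning number, not a Day 238 or Day 365 count. The figures show what could happen and are not a forecast.

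Finally, the SAP allows an analysis that includes excluded samples, profiles that mark them, and graphs for participants with symptoms or confirmed infection. These are optional and do not decide which samples belong in the PPI set.

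**Conclusion.** The point holds as an internal inconsistency. The lead sentence and the bullet of SAP section 4 define different PPI sets if the bullet is taken literally, and the literal version departs from protocol 9.3. Followed literally, it would keep roughly 95% to 98% of the Day 238 and Day 365 samples taken after a detected infection (uniform infection dates from Day 85). The possible distortion of a group GMT is 7% to 37% under the assumed 4- to 10-fold boost in 1 to 3 of 22 participants, and zero if no participant is infected or boosted.

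The documents do not show that boosted samples will be kept; that follows from one reading only. What is certain is the 7-day look-back, which is new in the SAP and not recorded as a change from the protocol.

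Severity is modest. No immunogenicity hypothesis is tested, longevity is exploratory, and the primary analysis covers data only to 28 days after Dose 2.

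**What to change.** Reword the SAP bullet along these lines: *samples collected from 7 days before the onset of the natural infection and at any time thereafter will not be considered*. This restores the protocol's open-ended forward exclusion and matches the SAP's lead sentence. Record the 7-day look-back in Appendix 2 as a change from the protocol, and check that the Data Presentation Specifications follow the same rule.

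The cost is one sentence and one appendix entry. The rule would still differ from the protocol by the look-back, so samples from the week before onset that the protocol would keep are lost. The SAP already drops them on either reading. They should be few: with onset uniform over Days 85 to 365, the look-back catches the Day 85 or Day 238 sample for (7 + 7)/280 = 5% of infections.
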